4.9 Dose Modifications

4.9.1 General Notes Regarding Dose Modification

Reasons for dose modification or delays, the supportive measures taken, and the outcomes will be documented in the CRF. The severity of adverse events will be graded according to the NCI CTCAE v5.0 grading system.

- For any concomintant conditions already apparent at baseline, the dose modifications will apply according to the corresponding shift in toxicity grade, if the investigator feels it is appropriate. For example, if a patient has Grade 1 asthenia at baseline that increases to Grade 2 during treatment, this will be considered a shift of one grade and treated as Grade 1 toxicity for dose-modification purposes.
- When several toxicities with different grades of severity occur at the same time, the dose modifications should be according to the highest grade observed.

Table 2 Recommended dose modifications for capecitabline:											
Toxicity (NCI	During a Course of Therapy	Dose Adjustment for Next									
Grade)		Treatment (% of starting dose)									
Grade 1	Maintain dose level	Maintain dose level									
Grade 2											
1 st appearance	Interrupt until resolved to	100%									
2 nd appearance	grade 0-1	75%									
3 rd appearance		50%									
4 th appearance	Discontinue treatment	-									
	permanently										
Grade 3											

4.9.2 Guidelines for Management of Adverse Events with Capecitabine Table 2 Recommended dose modifications for capecitabine:

1 st appearance	Interrupt until resolved to	75%
2 nd appearance	grade 0-1	50%
3 rd appearance	Discontinue treatment	-
	permanently	
Grade 4		
1 st appearance	Discontinue permanently	50%
	OR	
	If investigator deems it to be in	
	the patient's best interest to	
	continue, interrupt until	
	resolved to grade 0-1	

4.9.3 Guidelines for Management of Adverse Events with Imatinib 4.9.3.1 Dose Adjustments for Hepatotoxicity and Non-Hematologic Adverse Reactions

- If elevations in bilirubin >3 X institutional ULN or in liver transaminases >5X institutional ULN, imatinib should be withheld until bilirubin levels have returned to a <1.5 X institutional ULN and transaminase levels to <2.5 X institutional ULN. Treatment may then be continued at a reduced dose (i.e. 400 mg to 300 mg or 800 mg to 600 mg).
- If a severe non-hematologic adverse reaction develops (such as severe hepatotoxicity or severe fluid retention), imatinib should be withheld until the event has resolved. Thereafter, treatment can be resumed as appropriate depending on the initial severity of the event.

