(7) Subjects who are initiated on an OncoTreat-prioritized drug will have an optional ontreatment 'pharmacodynamic' biopsy performed within one month of initiating treatment and within 24 hours of the most recent dose. This biopsy will be performed as 'proof-of-principle' that OncoTreat prioritized drugs result in collapse of the master regulator architecture (also known as master regulator signature) of the tumor, *in vivo*.

(8) Peripheral blood will be drawn for routine laboratory testing, tumor markers (CA 19-9), and research testing for biomarker analysis. Pharmacology measurements will also be drawn weekly during Cycle 1 of treatment. [name], the Director of Clinical Pharmacology and Toxicology Laboratory (CPTL), will make available CLIA assays for every FDA-approved drug and will provide assays for any investigational agents that match to the subjects in the study. Pharmacokinetic (PK) results and toxicity may be used by the treating physician, after discussion with the Investigator, to modify dosing schedule as appropriate.

(9) Adverse events will be monitored and recorded (Section 8).

(10) Subjects will undergo routine standard-of-care radiographic assessments (CT preferred) at baseline and every 8 weeks with response measured per RECIST v1.1 (Section 10).

(11) Subjects will continue on study treatment until radiographic disease progression or death, intolerance to the study drug, or withdrawal of consent. Patients will not be permitted to continue study treatment after disease progression per RECIST v1.1 criteria (Section 10).

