4.3 Study Drugs

4.3.1 Capecitabine

The cycle length will be 21 days, and 1000 mg/m^2 given orally twice per day, usually separated 12 hours apart, on Days 1-14 of a 21-day cycle. Capecitabine should be taken with water within 30 minutes after a meal.

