4.9.3.2 Dose Adjustment for Hematologic Adverse Reactions

Dose reduction or treatment interruptions for severe neutropenia and thrombocytopenia are recommended if ANC <1,000 and/or platelets <50,000. First, stop imatinib until ANC \geq 1,500 and platelets \geq 75,000. Next, resume treatment with imatinib at the original starting dose of 400 mg or 600 mg (including if previously taking 800 mg). If the recurrence of ANC <1,000 and/or platelets <50,000, repeat step 1 and resume imatinib at a reduced dose (300 mg if starting dose was 400 mg, 400 mg if starting dose was 600 mg or 800 mg).

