4.9.3.3 Dose Modifications for Concomitant Strong CYP3A4 Inhibitors

The use of concomitant strong CYP3A4 inducers should be avoided (e.g., dexamethasone, phenytoin, carbamazepine, rifampin, rifabutin, rifampicin, phenobarbital). If patients must be co-administered a strong CYP3A4 inducer, based on pharmacokinetic studies, the dosage of imatinib should be increased by at least 50%, and clinical response should be carefully monitored.

4.9.4 Guidelines for Management of Adverse Events with Ruxolitinib 4.9.4.1 Dose Modification Guidelines for Thrombocytopenia

Treatment Interruption: Interrupt treatment for platelets less than 50,000. After recovery of platelet counts above this level, dosing may be restarted or increased following recovery of platelet counts to acceptable levels. Table 3 illustrates the maximum allowable dose that may be used in restarting ruxolitinib after a previous discontinuation.

Table 5. Maximum Restarting Doses	a for Kuxontinio After Safety Interruption			
Current Platelet Count	Maximum Dose When Restarting			
	Ruxolitib Treatment*			
Greater than or equal to 125,000	20 mg twice daily			
100,000 to less than 125,000	15 mg twice daily			
75,000 to less than 100,000	10 mg twice daily for at least 2 weeks; if			
	stable, may increase to 15 mg twice daily			
50,000 to less than 75,000	5 mg twice daily for at least 2 weeks; if			
	stable, may increase to 10 mg twice daily			
Less than 50,000	Continue hold			
*Maximum doses are displayed. When resta	rting, begin with a dose at least 5 mg twice			
daily below the dose at interruption.				

Table 3: Maximum Restarting Doses for Ruxolitinib After Safety Interruption

Dose Reductions: Dose reductions should be considered if the platelet counts decrease as outlined in Table 4 with the goal of avoiding dose interruptions for thrombocytopenia.

		Dose at T	ime of Platel	of Platelet Decline				
Platelet Count	25 mg twice daily	20 mg twice daily	15 mg twice daily	10 mg twice daily	5 mg twice daily			
	New Dose	New Dose	New Dose	New Dose	New Dose			
100,000 to less than 125,000	20 mg twice daily	15 mg twice daily	No change	No change	No change			
75,000 to less than 100,000	10 mg twice daily	10 mg twice daily	10 mg twice daily	No change	No change			
50,000 to less than 75,000	5 mg twice daily	5 mg twice daily	5 mg twice daily	5 mg twice daily	No change			
Less than 50,000	Hold	Hold	Hold	Hold	Hold			

Table 4:Dosing Recommendations for Thrombocytopenia

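### Capecitabine Table 2 sets the next dose from the starting dose with no ceiling at the current dose, so a new, milder toxicity can raise a reduced dose (750 to 1000 or 500 to 1000 mg/m2 twice daily); imatinib has a similar gap (300 to 400 mg)

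*Combined protocol and SAP*

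**What the plan says.** **Capecitabine.** Section 4.3.1 sets 1000 mg/m2 twice daily, "12 hours apart, on Days 1-14 of a 21-day cycle". Table 2 in section 4.9.2 gives the dose after each toxicity by grade and by number of appearances, under the column heading "Treatment (% of starting dose". Grade 1 leaves the dose level unchanged. Grade 2 runs 100%, 75%, 50%, then stop. Grade 3 runs 75%, 50%, then stop. Grade 4 means stopping or, if the investigator judges it best to continue, 50%.

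The only rule for differing grades is in section 4.9.1: "When several toxicities with different grades of severity occur at the same time, the dose modifications should be according to the highest grade observed". It covers simultaneous events and does not address a later one.

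**Imatinib.** After hepatotoxicity, section 4.9.3.1 says: "Treatment may then be continued at a reduced dose (i.e. 400 mg to 300 mg or 800 mg to 600 mg". After a severe non-hematologic reaction it says: "Thereafter, treatment can be resumed as appropriate depending on the initial severity of the event". After a first neutropenia or thrombocytopenia, section 4.9.3.2 says to "resume treatment with imatinib at the original starting dose of 400 mg or 600 mg (including if previously taking 800 mg". On recurrence it gives 300 mg if the starting dose was 400 mg, and 400 mg if it was 600 or 800 mg.

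**Ruxolitinib.** The footnote to Table 3 in section 4.9.4.1 requires restart at least 5 mg twice "daily below the dose at interruption".

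**Discretion.** Table 2 is titled as recommended modifications. Section 4.1, item 8, adds: "Pharmacokinetic (PK) results and toxicity may be used by the treating physician, after discussion with the Investigator, to modify dosing schedule as appropriate".

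**The concern.** Table 2 works for repeats of one grade of one toxicity, where the dose only falls. It has no rule for a subject already on a reduced dose who then has a different, milder toxicity. Because each percentage refers to the starting dose, the row for the new event can give a dose above the current one.

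The ordering shows that this is unlikely to be intended. A subject on 75% who has a Grade 1 event stays on 75%. The same subject with a first Grade 2 event is sent to 100%, so the worse event earns the higher dose.

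At stake is dosing safety for a few subjects: a rise prompted by a new toxicity, in someone already reduced for a more severe one.

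**Working it through.** The plan states no figure to reproduce here. The check applies the rules as written.

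**Capecitabine dose per administration** = Table 2 percentage × 1000 mg/m2. **Exposure per course** = 2 doses a day × 14 days × dose.

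| Sequence (last event is a first Grade 2 of a different toxicity) | Dose before | Dose assigned | Change per dose | Exposure per course |
|---|---|---|---|---|
| Grade 3, then Grade 2 | 0.75 × 1000 = 750 | 1.00 × 1000 = 1000 | +250 (250/750 = 33%) | 21,000 to 28,000 mg/m2 |
| Two Grade 3 events, then Grade 2 | 0.50 × 1000 = 500 | 1000 | +500 (100%) | 14,000 to 28,000 mg/m2 |
| Grade 4 (treatment continued), then Grade 2 | 500 | 1000 | +500 (100%) | 14,000 to 28,000 mg/m2 |

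A full enumeration of Table 2 sequences, with a separate counter for each grade, also finds 500 to 750 mg/m2 steps, for example a first Grade 3 event after a Grade 4 event.

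**How appearances are counted.** The protocol does not define this, so the Grade 3 then Grade 2 path was tried under each reading.

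- *Counted per toxicity.* A Grade 2 of a different toxicity is a first appearance: 100%. The dose rises.
- *Counted per grade across toxicities, peak grade only.* With no earlier Grade 2 event it is a first appearance: 100%. The dose rises.
- *Grades passed through also count.* Section 8.3 requires every grade change within an episode to be recorded. If a Grade 3 episode that passes through Grade 2 uses up one Grade 2 appearance, a later Grade 2 of the same toxicity is a second appearance: 75%, no rise. After two such episodes it is a third: 50%, again no rise. For a different toxicity this protects the subject only if appearances are also pooled across toxicities.

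**Imatinib.** Starting dose 400 mg (section 4.3.2).

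- 400 mg, hepatotoxicity, 300 mg (optional cut); first cytopenia, resume at 400 mg. Change 100/300 = +33%.
- After escalation to 800 mg: first cytopenia, 400 mg; hepatotoxicity, 300 mg; second cytopenia, 400 mg. This takes 800 mg as the starting dose in the recurrence rule. Other long sequences end in the same step.

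The discretion in 4.9.3.1 concerns restart after the non-hematologic event. It does not address a later cytopenia.

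**Reach.** Section 4.6.1 cites dose reductions in 16 to 34% of patients at this capecitabine starting dose. Applying that here is an assumption. Expected treated subjects are 9 (section 12) to 15 (synopsis).

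- All on capecitabine: 9 × 0.16 = 1.4 to 15 × 0.34 = 5.1 with any reduction.
- One third on capecitabine (assumption): 3 × 0.16 = 0.5 to 5 × 0.34 = 1.7.

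These count subjects with any reduction. Those who then meet an upward step are a subset, and the documents give no rate for it.

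**With a ceiling at the dose at interruption**, the three tabulated sequences end at 750, 500 and 500 mg/m2. In the enumeration, none of 188 steps raises the dose. The imatinib sequences stay at 300 mg.

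**The case against.** **Discretion.** These are guidelines, and toxicity may guide dosing after discussion with the investigator. Nothing compels a clinician to restore 1000 mg/m2. This stands, and it limits the harm. But discretion only allows departure from the printed dose, and the printed dose is the less cautious one.

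**Counting.** A reader might infer that every Grade 2 event after a Grade 3 reduction restores full dose. The documents do not support that: for the same toxicity, counting each recorded grade makes the table coherent. That objection stands for the same toxicity. It does not dispose of the point, because section 8.3 is a recording rule rather than a dosing rule, and a different toxicity still reads 100% when counted per toxicity.

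**The package insert.** Section 4.1, item 6, aligns dose and schedule with the insert. It does not mention dose-modification rules, and the insert is not among the documents, so it cannot be relied on to fill the gap.

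**Reach.** A reader might take 1.4 to 5.1 as the number of subjects re-escalated. It is not. The cited trials behind 16 to 34% were in breast cancer, and one gave capecitabine with sorafenib. Time on treatment may also be short: section 3.1 gives median PFS of 1.5 months on 5-fluorouracil alone, about two 21-day cycles. Grade 3, recovery, restart and a new Grade 2 would have to fit within that. The number affected may be zero or one.

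**Imatinib.** The hepatic cut is optional, and the path needs both hepatotoxicity and a marked cytopenia in one subject. It is rare, but the text has no answer when it happens.

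**Conclusion.** The gap is real. Followed exactly, Table 2 raises a reduced capecitabine dose after a first Grade 2 event of a different toxicity: 750 to 1000 mg/m2 twice daily after one Grade 3 event, and 500 to 1000 after a cut to 50%. This assumes that appearances are counted per toxicity, or per grade at peak grade. For the same toxicity the outcome is undetermined, because the counting rule is not given. Imatinib has a matching 300 to 400 mg step, by more than one route once 800 mg has been used.

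The importance is minor to modest. The rise never exceeds the starting dose, physicians can avoid it, and few or no subjects may meet it. A reader might infer that the safety endpoint or the trial's conclusions are compromised. The documents do not support that: no endpoint definition, sample size or analysis depends on this rule.

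**What to change.** Under Table 2 add: *After any toxicity, the next capecitabine dose must be no higher than the dose at interruption, whatever percentage Table 2 gives; the investigator may reduce further.*

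In section 4.9.3.2 add, for both the first event and recurrence: *but no higher than the dose at interruption if the dose was already reduced for toxicity.*

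The wording should be a ceiling. Fixing the dose at the lower of the two values would hold a subject at 75% when a first Grade 3 event follows a second Grade 2 event, where a further step down may be wanted. The ceiling leaves the same-grade step-downs as they are, does not forbid re-escalation for other reasons, and works however appearances are counted.

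The cost is one sentence and one clause in a protocol amendment, with no extra subjects, visits or procedures.

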4.9.3.2 Dose Adjustment for Hematologic Adverse Reactions

Dose reduction or treatment interruptions for severe neutropenia and thrombocytopenia are recommended if ANC <1,000 and/or platelets <50,000. First, stop imatinib until ANC \geq 1,500 and platelets \geq 75,000. Next, resume treatment with imatinib at the original starting dose of 400 mg or 600 mg (including if previously taking 800 mg). If the recurrence of ANC <1,000 and/or platelets <50,000, repeat step 1 and resume imatinib at a reduced dose (300 mg if starting dose was 400 mg, 400 mg if starting dose was 600 mg or 800 mg).

4.9.3.3 Dose Modifications for Concomitant Strong CYP3A4 Inhibitors

The use of concomitant strong CYP3A4 inducers should be avoided (e.g., dexamethasone, phenytoin, carbamazepine, rifampin, rifabutin, rifampicin, phenobarbital). If patients must be co-administered a strong CYP3A4 inducer, based on pharmacokinetic studies, the dosage of imatinib should be increased by at least 50%, and clinical response should be carefully monitored.

4.9.4 Guidelines for Management of Adverse Events with Ruxolitinib 4.9.4.1 Dose Modification Guidelines for Thrombocytopenia

Treatment Interruption: Interrupt treatment for platelets less than 50,000. After recovery of platelet counts above this level, dosing may be restarted or increased following recovery of platelet counts to acceptable levels. Table 3 illustrates the maximum allowable dose that may be used in restarting ruxolitinib after a previous discontinuation.

Table 5. Maximum Restarting Doses	a for Kuxontinio After Safety Interruption			
Current Platelet Count	Maximum Dose When Restarting			
	Ruxolitib Treatment*			
Greater than or equal to 125,000	20 mg twice daily			
100,000 to less than 125,000	15 mg twice daily			
75,000 to less than 100,000	10 mg twice daily for at least 2 weeks; if			
	stable, may increase to 15 mg twice daily			
50,000 to less than 75,000	5 mg twice daily for at least 2 weeks; if			
	stable, may increase to 10 mg twice daily			
Less than 50,000	Continue hold			
*Maximum doses are displayed. When resta	rting, begin with a dose at least 5 mg twice			
daily below the dose at interruption.				

Table 3: Maximum Restarting Doses for Ruxolitinib After Safety Interruption

Dose Reductions: Dose reductions should be considered if the platelet counts decrease as outlined in Table 4 with the goal of avoiding dose interruptions for thrombocytopenia.

		Dose at T	ime of Platel	of Platelet Decline				
Platelet Count	25 mg twice daily	20 mg twice daily	15 mg twice daily	10 mg twice daily	5 mg twice daily			
	New Dose	New Dose	New Dose	New Dose	New Dose			
100,000 to less than 125,000	20 mg twice daily	15 mg twice daily	No change	No change	No change			
75,000 to less than 100,000	10 mg twice daily	10 mg twice daily	10 mg twice daily	No change	No change			
50,000 to less than 75,000	5 mg twice daily	5 mg twice daily	5 mg twice daily	5 mg twice daily	No change			
Less than 50,000	Hold	Hold	Hold	Hold	Hold			

Table 4:Dosing Recommendations for Thrombocytopenia

4.9.4.2 Dose Modification Based on Response

If efficacy is considered insufficient and platelet and neutrophil counts are adequate, doses may be increased in 5 mg twice daily increments to a maximum of 25 mg twice daily. Doses should not be increased during the first 4 weeks of therapy and not more frequently than every 2 weeks.

4.9.4.3 Dose Adjustment with Concomitant Strong CYP3A4 Inhibitors

On the basis of pharmacokinetic studies in healthy volunteers, when administering ruxolitinib with strong CYP3A4 inhibitors (such as but not limited to boceprevir, clarithromycin, conivaptan, grapefruit juice, indinavir, itraconazole, ketoconazole, lopinavir/ritonavir, mibefradil, nefazodone, nelfinavir, posaconazole, ritonavir, saquinavir, telaprevir, telithromycin, voriconazole), the recommended starting dose is 10 mg twice daily for patients with a platelet count greater than or equal to 100,000. Additional dose modifications should be made with careful monitoring of safety and efficacy.

5. SUBJECT SELECTION AND WITHDRAWAL

Male and female subjects with locally advanced, unresectable or metastatic pancreatic ductal adenocarcinoma after progression on first- or second-line systemic therapy who are considered incurable will be enrolled on this trial.

5.1 Inclusion Criteria

In order to be eligible for participation in this trial, the subject must:

- Be willing and able to provide written informed consent for the trial.
- Age ≥ 18 years of age on day of signing informed consent.
- Have histologically or cytologically confirmed diagnosis of pancreatic ductal adenocarcinoma.
- Have a predicted life expectancy of greater than 3 months.
- Have measurable disease based on RECIST v1.1.
- Have a performance status of 0 or 1 using the ECOG Performance Scale
- Have documented radiographic or clinical progression to or documented intolerance to 5-FU- or gemcitabine-based systemic therapy for locally advanced, unresectable or metastastic disease. Patients for whom targeted therapy.
- MSI-H/dMMR or NTRK-fusion positive tumors
 - Subjects must have received prior treatment with approved drugs for tumors harboring these aberrations.
- Have a negative urine or serum pregnancy test within 72 hours prior to receiving the first dose of study medication (female subjects of childbearing potential). If the urine test is positive or cannot be confirmed as negative, a serum pregnancy test will be required.
- Be willing to use an adequate method of contraception for the course of the study through 120 days after the last dose of study medication (male and female subjects of childbearing potential).
- Demonstrate adequate organ function as defined below in Table 5.

Table 5Adequate Organ Function Laboratory Values

	0	e e
System		Laboratory Value

Hematological	
Leukocytes	≥2,000 /mcL
Absolute neutrophil count (ANC)	≥1,500 /mcL
Platelets	≥100,000 /mcL
Hemoglobin	≥9 g/dL without transfusion or EPO
	dependency within 7 days
Renal	
Creatinine OR	\leq 1.5 X upper limit of normal (ULN) OR
Measured or calculated ^a creatinine	\geq 60 mL/min for subject with creatinine levels
clearance (GFR can also be used in	>1.5 X institutional ULN
place of creatinine or CrCl)	
Hepatic	
Total bilirubin	$\leq 2 \text{ mg/dL}$ or direct bilirubin $\leq \text{ULN}$ for those
	with total bilirubin >2 X ULN
	Subjects with Gilbert Syndrome will be
AST (SCOT) and ALT (SCDT)	eligible if total bilirubin is $<3.0 \text{ mg/dL}$
ASI (SGOI) and ALI (SGPI)	<2.5 X ULN OR <5 X ULN for subjects with liver metastases
Albumin	>3.0 mg/dL
Coagulation	
Coagulation	
INR or PT	≤1.5 X ULN unless subject is receiving
aPTT	anticoagulant therapy as long as PT or aPTT
	is within therapeutic range of intended use of
	anticoagulants

5.2 Exclusion Criteria

The subject must be excluded from participating in the trial if the subject:

- Is currently participating and receiving study therapy or has participated in a study of an investigational agent and received study therapy, or herbal/complementary oral or IV medicine, within 2 weeks of the first dose of treatment.
- All toxicities attributed to prior anti-cancer therapy other than alopecia and fatigue must have resolved to Grade 1 (NCI CTCAE v4.0) or baseline prior to administration of first dose of study drug. Subjects with toxicities attributed to prior anti-cancer therapy that are not expected to resolve and result in long-lasting sequalae, such as chronic neuropathy after platinum-based therapy, are permitted to enroll.

- Has received chemotherapy or radiotherapy within 14 days of first dose of study medication.
- Has a solid organ or hematologic transplant.
- Has experienced weight loss >10% over 2 months prior to first dose of study therapy.
- Has a diagnosed additional malignancy within 2 years prior to first dose of trial treatment with the exception of curatively treated basal cell carcinoma of the skin, squamous cell carcinoma of the skin or curatively resected in situ breast cancers. Subjects with another malignancy diagnosed >2 years prior to the first dose of trial medication who were treated with curative intent and are not undergoing active therapy will be eligible.
- Has an active infection requiring systemic therapy.
- Has clinically relevant ascites (defined as requiring paracentesis within 21 days of first dose of study drug) or with moderate radiographic ascites. A minimal amount of radiographic ascites is allowed.
- Has a history or current evidence of any condition, therapy, or laboratory abnormality that might confound the results of the trial, interfere with the subject's participation for the full duration of the trial, or is not in the best interest of the subject to participate, in the opinion of the investigator, including dialysis.
- Has a known psychiatric or substance abuse disorders that would interfere with cooperation with the requirements of the trial.
- Is pregnant or breastfeeding, or expecting to conceive or father children within the projected duration of the trial, starting with the screening visit through 120 days after the last dose of trial treatment.

